7.2.2.1. Treatment-Emergent Laboratory Abnormalities

Treatment-emergent laboratory abnormalities are defined as values that increase at least 1 toxicity grade from baseline at any postbaseline time point, up to and including the date of last dose of study drug plus 30 days. If the relevant baseline laboratory value is missing, any abnormality of at least Grade 1 observed within the time frame specified above will be considered treatment emergent.

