4.2. Inclusion Criteria

Participants must meet all of the following inclusion criteria to be eligible for participation in this study:

- 1) SARS-CoV-2 positive as determined by polymerase chain reaction (PCR) or other commercially available or public health assay (eg, nucleic acid amplification test and antigen tests) in any respiratory specimen
- 2) Hospitalized for COVID-19
- 3) Age \geq 12 years and weighing at least 40 kg
- 4) O₂ saturation \leq 94% on room air or requiring O₂ supplementation OR radiographic evidence of pulmonary infiltrates for COVID-19
- 5) Have either:
 - a) Severely reduced kidney function (eGFR $<$ 30 mL/min/1.73 m²), using the Chronic Kidney Disease Epidemiology Collaboration (CKD-EPI) and revised Schwartz equations for adults and adolescents, respectively, including people with ESKD requiring chronic dialysis but not people requiring RRT for AKI {[Levey 2009](#), [Schwartz 2009](#)}

Adults: $eGFR \text{ (mL/min/1.73 m}^2\text{)} = 141 \times \min(\text{SCr}/\kappa, 1)^\alpha \times \max(\text{SCr}/\kappa, 1)^{-1.209} \times 0.993^{\text{Age}} \times 1.018 \text{ [if female]} \times 1.159 \text{ [if African American]}$

$\kappa = 0.7$ for females; 0.9 for males

$\alpha = -0.329$ for females; -0.411 for males

Adolescents (age 12–17 years): $eGFR \text{ (mL/min/1.73 m}^2\text{)} = (0.41 \times \text{Height in cm}) / \text{SCr}$

SCr in mg/dL, age in years

(See [Appendix 7](#) for web links to adult and adolescent eGFR calculators), OR

- b) Ongoing AKI: defined as a 50% increase in SCr within a 48-hour period that is sustained (ie, requires confirmatory SCr) for ≥ 6 hours despite supportive care
- 6) Willing and able to provide written informed consent, or with a legal representative who can provide informed consent, or enrolled under International Council for Harmonisation (of Technical Requirements for Pharmaceuticals for Human Use) (ICH) E6(R2) 4.8.15 emergency use provisions as deemed necessary by the investigator (age ≥ 18) prior to performing study procedures
- 7) The interval between COVID-19 symptoms onset and randomization is no more than 10 days
- 8) Male participants and female participants of childbearing potential who engage in heterosexual intercourse must agree to use protocol-specified method(s) of contraception as described in [Appendix 4](#)

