5. INVESTIGATIONAL MEDICINAL PRODUCTS

5.1. Randomization, Blinding, and Treatment Codes Access

5.1.1. Randomization

Participants who meet screening and randomization eligibility criteria will be randomized in a 2:1 ratio to RDV or saline as placebo starting on Day 1 and assigned a participant number. Randomization will be stratified by:

- ESKD requiring chronic dialysis
- High-flow oxygen requirement
- Region (US vs ex-US)

No more than 20% of enrolled participants will have ESKD requiring chronic dialysis.

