7.2.2. Graded Laboratory Values

The DAIDS Table for Grading the Severity of Adult and Pediatric Adverse Event, Version 2.1 (July 2017) (see Section 7.1.2) will be used for assigning toxicity grades (0 to 4) to laboratory results for analysis. Grade 0 includes all values that do not meet the criteria for an abnormality of at least Grade 1. For laboratory tests with criteria for both increased and decreased levels, analyses for each direction (i.e., increased, decreased) will be presented separately.

For baseline, if both central lab and local lab results are available, then central lab results will be used to determine baseline toxicity grade; local lab results will only be used if central lab results are missing. For postbaseline laboratory abnormalities, both central lab and local lab results will be used.

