7.2.2.2. Summaries of Laboratory Abnormalities

Laboratory data that are categorical will be summarized using the number and percentage of participants in the study with the given response at baseline and each scheduled postbaseline visit.

The following summaries (number and percentage of participants) for treatment-emergent laboratory abnormalities will be provided by lab test and treatment group; participants will be categorized according to the most severe postbaseline abnormality grade for a given lab test:

- Treatment-emergent laboratory abnormalities
- Treatment-emergent Grade 3 or 4 laboratory abnormalities

For all summaries of laboratory abnormalities, the denominator is the number of participants with nonmissing postbaseline values up to 30 days after last dosing date.

A by-participant listing of treatment-emergent Grade 3 or 4 laboratory abnormalities will be provided by participant ID number and visit in chronological order.

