- If the latest clinical date falls into the same year, but a prior month of death, then the 1st of the month of death will be the imputed date of death;
- If the latest clinical date falls into a prior year of death, then the 1st of the month of death will be the imputed date of death.

19) The precision in reporting numerical values should be as follows:

Raw measurements will be reported the same as the data captured electronically or on the eCRF.

Standard deviation and standard error will be reported to one more significant decimal place than the raw measurement.

Mean, median, minimum, Q1, Q3, maximum, 95% CIs will be reported to the same number of decimal places of the raw measurements.

If records for the same lab use different decimal places, the decimal place with majority records would be used.

Exceptions may be considered.

20) Graded Laboratory Abnormalities Summary

The following labels will be used for laboratory abnormalities and Grade 3 or 4 laboratory abnormalities summary tables and listings:

Battery	Lab Test Label Used in l-labtox Listing	Toxicity Direction	Lab Test Label Used in t-labtox Table
Hematology	Hemoglobin	Decrease	Hemoglobin (Decreased)
	Lymphocytes	Decrease	Lymphocytes (Decreased)
	Neutrophils	Decrease	Neutrophils (Decreased)
	Platelets	Decrease	Platelets (Decreased)
	WBC	Decrease	WBC (Decreased)
Chemistry	Albumin	Decrease	Albumin (Decreased)
	Alkaline Phosphatase	Increase	Alkaline Phosphatase (Increased)
	ALT	Increase	ALT (Increased)
	AST	Increase	AST (Increased)
	Bicarbonate	Decrease	Bicarbonate (Decreased)
	Corrected Calcium	Increase	Corrected Calcium (Hypercalcemia)
	Corrected Calcium	Decrease	Corrected Calcium (Hypocalcemia)
	Creatine Kinase (CK)	Increase	Creatine Kinase (Increased)
	Creatinine	Increase	Creatinine (Increased)
	Lipase	Increase	Lipase (Increased)
	Magnesium	Decrease	Magnesium (Hypomagnesemia)
	Phosphate	Decrease	Phosphate (Hypophosphatemia)
	Serum Glucose	Increase	Serum Glucose (Hyperglycemia)
	Serum Glucose	Decrease	Serum Glucose (Hypoglycemia)
	Serum Potassium	Increase	Serum Potassium (Hyperkalemia)
	Serum Potassium	Decrease	Serum Potassium (Hypokalemia)
	Serum Sodium	Increase	Serum Sodium (Hypernatremia)
	Serum Sodium	Decrease	Serum Sodium (Hyponatremia)
	Total Bilirubin	Increase	Total Bilirubin (Hyperbilirubinemia)
Uric Acid	Increase	Uric Acid (Hyperuricemia)	
Coagulation	Prothrombin Intl. Normalized Ratio (INR)	Increase	Prothrombin Intl. Normalized Ratio (Increased)

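### Participants at creatinine Grade 4 at baseline cannot have a treatment-emergent creatinine abnormality but stay in the denominator, which dilutes that row of the graded laboratory table

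*SAP*

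**What the plan says.** SAP 7.2.2 states that the DAIDS table "will be used for assigning toxicity grades (0 to 4) to laboratory results for analysis". SAP 7.2.2.1 counts as treatment-emergent "values that increase at least 1 toxicity grade from baseline at any postbaseline time point", up to 30 days after the last dose. Protocol 8.6.3 has the same one-grade rule. For every abnormality summary, SAP 7.2.2.2 says that "the denominator is the number of participants with nonmissing postbaseline values up to 30 days after last dosing date", with no condition on baseline grade. Creatinine, in the increase direction, is one of the graded tests in SAP Appendix 2, item 20.

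Protocol 4.2 admits participants by two routes. Route 5a is eGFR below 30 mL/min/1.73 m², "including people with ESKD requiring chronic dialysis but not people requiring RRT for AKI". Route 5b is "Ongoing AKI: defined as a 50% increase in SCr within a 48-hour period", confirmed as sustained; it sets no minimum creatinine. Protocol 5.1.1 adds: "No more than 20% of enrolled participants will have ESKD requiring chronic dialysis".

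SAP 7.2 plans a sensitivity analysis of serum creatinine (SCr) and BUN. It leaves out participants on RRT at baseline, and it drops records from the start of any later RRT until 3 days after its end. No visible text deals with a baseline value already at the top grade.

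**The concern.** The one-grade rule works where most participants start at Grade 0 or 1. Here eligibility route 5a selects for high creatinine. Someone at Grade 4 on Day 1 would need a Grade 5 to count, so even a doubling of creatinine adds nothing to the numerator while the participant still adds one to the denominator.

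Kidney safety is a central question for this trial. Protocol 1.3 explains that the excipient SBECD is renally cleared and accumulates when kidney function is reduced, and that tubular injury was seen in nonclinical studies. A creatinine row with diluted percentages, and no indication of how many participants could not contribute, would look more reassuring than the data warrant.

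**Working it through.** The plan states no figure for this row, so there is nothing to reproduce. The check has four steps.

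**1. The ceiling.** Top grade = 4 (SAP 7.2.2). An event needs at least baseline grade + 1 (SAP 7.2.2.1). With baseline grade 4 the requirement is 5, which does not exist. Section 7.2.2.2 keeps the participant in the denominator.

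**2. Can eligible participants start there?** Inverting the protocol's adult CKD-EPI equation for SCr above κ (without the race factor):

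SCr = κ × (141 × 0.993^age × [1.018 if female] / eGFR)^(1/1.209), with κ = 0.9 for men and 0.7 for women.

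| Age 60 | eGFR 30 | eGFR 15 | eGFR 10 |
|---|---|---|---|
| Men, SCr mg/dL | 2.28 | 4.05 | 5.67 |
| Women, SCr mg/dL | 1.80 | 3.20 | 4.47 |

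The documents link to the DAIDS scale but do not reproduce its creatinine cut-offs or the ULN. Assume grading by absolute level, Grade 4 starting somewhere from 2.5 to 5 × ULN, and a ULN of 1.2 to 1.3 mg/dL for men and 1.0 to 1.1 for women. A 60-year-old then starts at Grade 4 once eGFR falls below a value between about 8 (woman, 5 × 1.1 = 5.5 mg/dL, eGFR 7.8) and about 22 (man, 2.5 × 1.2 = 3.0 mg/dL, eGFR 21.6). That whole range is eligible under route 5a.

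ESKD alone could supply at most 0.20 × 1116 = 223 participants if all were at Grade 4. Enrollment stopped before 50% (SAP 2.4), so applying the cap to 558 gives 0.20 × 558 = 111.6, that is, fewer than 112. Undialysed advanced kidney disease would add to this by an unknown amount.

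**3. Dilution with equal shares.** Let f be the share of each arm's denominator at baseline Grade 4. Reported rate = (1 - f) × rate among those able to have an event. With assumed at-risk rates of 30% vs 20%:

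| f (assumed) | Reported rates | Difference (points) | Risk ratio |
|---|---|---|---|
| 5% | 28.5% vs 19% | 9.5 | 1.5 |
| 20% | 24% vs 16% | 8 | 1.5 |
| 40% | 18% vs 12% | 6 | 1.5 |
| 60% | 12% vs 8% | 4 | 1.5 |

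The factor (1 - f) cancels in the ratio but not in the percentages or the difference.

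**4. Unequal shares.** With no drug effect and an at-risk rate of 20% in both arms, f of 30% vs 20% gives 0.20 × 0.70 = 14% vs 0.20 × 0.80 = 16%, a spurious ratio of 0.875. Reversing the imbalance gives 16% vs 14%, a ratio of 1.14. Randomization is stratified by ESKD, but not by the severity of undialysed kidney disease.

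**The case against.** The case on the other side is substantial.

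- **Size.** The cut-offs, the ULN, the share at Grade 4 and the event rates above are all assumptions. This stands: the documents show that the dilution exists wherever anyone starts at Grade 4, but not how large it is.
- **Population.** A reader might infer that the whole trial sits at the top of the scale. The documents do not support that. Route 5b sets no SCr floor, ESKD is capped at 20%, and under most of the assumed cut-offs a participant with eGFR in the 20s starts below Grade 4.
- **Other renal information.** A reader might also infer that renal toxicity would go unseen. That is not supported either. Numeric SCr change from baseline is summarized and tested (SAP 7.2.1), peak SCr is derived for participants without ESKD (Appendix 2, item 17), RRT-free days are compared in the same group (SAP 6.2.1), and renal adverse events and RRT are listed (SAP 7.1.6 and 7.5). None of these has a grade ceiling. Redacted sections may hold more.
- **RRT sensitivity analysis.** It takes out most dialysis participants. This stands in part: the text does not say whether it extends to the graded tables, and it leaves in undialysed participants at Grade 4.
- **Bias between arms.** With equal shares the risk ratio is unaffected, and stratification by ESKD supports balance. The unequal example is illustrative and is not evidence of an imbalance. The graded table is also descriptive, with no test planned, so loss of power is not the issue.

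**Conclusion.** The point holds, and it is limited to one row. Under SAP 7.2.2.1 and 7.2.2.2, participants at creatinine Grade 4 at baseline dilute that row's percentages and risk difference by the factor (1 - f), where f is not given in the documents. The risk ratio is correct if f is equal in both arms and biased if it is not. That participants can start at Grade 4 rests on the eligibility criteria and an assumed cut-off between 2.5 and 5 × ULN; the conclusion does not depend on where in that range the cut-off lies, but the size does. The rest of the renal safety assessment is not undermined. This is a cheap improvement to a stated rule.

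**What to change.** In SAP 7.2.2.2, for creatinine:

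1. Show baseline creatinine grade by arm.
2. Keep the planned row. Beside it add an at-risk row whose denominator is participants with baseline grade below 4 and not on RRT at baseline, and give the number excluded by arm.
3. For participants not on RRT at baseline, add by-arm counts of peak postbaseline SCr ≥ 1.5, > 2 and > 3 × baseline, or start of RRT. Follow the AKI staging footnote to Protocol Table 1, including its further route to Stage 3: SCr ≥ 4.0 mg/dL with an acute rise of at least 0.5 mg/dL. That route matters because tripling is hard to reach from a high starting value. RRT starts must count as events, because the existing sensitivity analysis drops SCr records from the start of RRT.

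No new data are needed: SCr is scheduled daily in hospital, RRT is assessed throughout, and a peak SCr derivation already exists for participants without ESKD. The cost is SAP wording, a smaller denominator for the added row, and one extra table. If the SAP is already final, Section 1 provides for documenting the change in the CSR.

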7.2.2.2. Summaries of Laboratory Abnormalities

Laboratory data that are categorical will be summarized using the number and percentage of participants in the study with the given response at baseline and each scheduled postbaseline visit.

The following summaries (number and percentage of participants) for treatment-emergent laboratory abnormalities will be provided by lab test and treatment group; participants will be categorized according to the most severe postbaseline abnormality grade for a given lab test:

- Treatment-emergent laboratory abnormalities
- Treatment-emergent Grade 3 or 4 laboratory abnormalities

For all summaries of laboratory abnormalities, the denominator is the number of participants with nonmissing postbaseline values up to 30 days after last dosing date.

A by-participant listing of treatment-emergent Grade 3 or 4 laboratory abnormalities will be provided by participant ID number and visit in chronological order.

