A dosing duration of up to 5 days will be evaluated in this study. The 5 days dosing duration is the recommended IV RDV duration for treatment of COVID-19 requiring hospitalization and not requiring invasive mechanical ventilation (IMV) and/or extracorporeal membrane oxygenation (ECMO) {[VEKLURY 2020](#)}. Moreover, patients with COVID-19 who do not require mechanical ventilation, 5 days of RDV showed similar efficacy to a 10-day regimen. Similarly, 5 days treatment of RDV in participants with moderate COVID-19 was associated with a significant improvement in clinical status compared with standard of care (SOC) and approximately a third of participants were discharged prior to completion of 5 days RDV therapy.

In order to fully characterize the relationship between kidney function and RDV disposition, an additional Phase 1 study in non-COVID-19 participants with chronic renal impairment (mild, moderate, severe chronic impairment, and end-stage renal disease) is ongoing (GS-US-540-9015). PK and safety data from both studies will be used to inform the recommendations for the use of RDV in COVID-19 patients with varying degrees of renal impairment.

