6.4. Assessments (Days 2 Through 29)

The following evaluations are to be completed daily (unless otherwise noted in indicated sections and [Appendix 3](#)) from Day 2 through Day 29 or until discharge from inpatient hospitalization, whichever is earlier. If the participant is readmitted to the hospital prior to Day 29, evaluation for RRT, ordinal scale and AEs are to be completed daily through Day 29.

Participants must complete the following assessments before being administered investigational drug:

- Vital signs (heart rate, temperature, blood pressure)
- Documentation of respiratory status:
 - Respiratory rate
 - Oxygenation: SpO₂, room air, low-flow O₂, high-flow O₂, CPAP/BIPAP, mechanical ventilation, venovenous ECMO, venoarterial ECMO, and target FIO₂. The target FIO₂ value applies to all forms of O₂ nasal and mask delivery (nasal prongs, masks, CPAP/BIPAP) as well as mechanical ventilation

- IMV (yes/no; if yes, provide date when mechanical ventilation was started)
- Assessment of need for RRT
- Record the 8-point ordinal scale (see Section 6.9)
- Review AEs and document concomitant medications
- Laboratory evaluations: Chemistry, hematology, coagulation, and SCr (see Section 6.5)

█ [REDACTED]

█ [REDACTED]

- Collection of nasopharyngeal swab sample for SARS-CoV-2 RT-qPCR testing CCI [REDACTED]
[REDACTED] (see Section 6.8)

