6.5. Additional Assessments

Laboratory testing during hospitalization will be performed according to SOC practice with results for chemistry, hematology, and any SARS-CoV-2 testing being reported to the sponsor.

In addition, even if not performed as SOC, the following will be completed at screening and on Days 1, 3, 5, 8, 12, 16, 20, 24, and 29 or until discharge, whichever is earlier:

- Laboratory evaluations: Chemistry, hematology, coagulation

In addition, even if not performed as SOC, the following will be completed at screening and on Days 1 through 29, or until discharge, whichever is earlier:

- Laboratory evaluations: SCr

CCI [REDACTED]

[REDACTED]

CCI [REDACTED]

CCI [REDACTED]

[REDACTED]

[REDACTED]

[REDACTED]

[REDACTED]

CCI [REDACTED]

[REDACTED]

[REDACTED] CCI [REDACTED] CCI [REDACTED]

[REDACTED]

CCI [REDACTED]

[REDACTED]

[REDACTED]

[REDACTED]

[REDACTED]

[REDACTED]

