6.10. Posttreatment Assessments

Upon discharge from inpatient hospitalization, the following assessments will be required at the Day 29 and Day 60 phone follow-up (see [Appendix 3](#)):

- Assessment of need for RRT
- Record the 8-point ordinal scale (see Section 6.9)
- Review AEs and document concomitant medications

- Mortality
- IMV (yes/no if yes, provide date when mechanical ventilation was started)
- Hospital readmission rate

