7.2.1. Summaries of Numeric Laboratory Results

Descriptive statistics will be provided by treatment group for selected laboratory test specified in the study protocol as follows:

- Baseline values
- Values at each postbaseline analysis visit
- Change from baseline at each postbaseline analysis visit
- Percentage change from baseline to each postbaseline analysis visit (if specified)

A baseline laboratory value will be defined as the last nonmissing measurement obtained on or prior to the date/time of first dose of study drug. Change from baseline to a postbaseline visit will be defined as the visit value minus the baseline value. The mean, median, Q1, Q3, minimum, and maximum values will be displayed to the reported number of digits; SD values will be displayed to the reported number of digits plus 1. Baseline and change from baseline will be compared between the treatment groups using the 2-sided Wilcoxon rank sum test.

In the case of multiple values in an analysis window, data will be selected for analysis as described in Section 3.8.3.

In an analysis window (including baseline window), if both central lab and local lab results are available, then central lab results will be used instead of local lab results; local lab results will only be used if central lab results are missing.

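### Required safety laboratories end at discharge, but graded abnormalities are counted per participant to last dose + 30 days, so unequal laboratory observation can shift the percentages, in either direction, with no drug effect

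*SAP*

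**What the plan says.** **Sampling.** Under protocol 6.5, chemistry, hematology and coagulation are required "on Days 1, 3, 5, 8, 12, 16, 20, 24, and 29 or until discharge, whichever is earlier". Serum creatinine is required daily, "completed at screening and on Days 1 through 29, or until discharge, whichever is earlier". For those who have left hospital, protocol 6.10 states: "Upon discharge from inpatient hospitalization, the following assessments will be required at the Day 29 and Day 60 phone follow-up". Its list covers dialysis need, ordinal scale, adverse events, medications, mortality, ventilation and readmission, but no laboratory test. On readmission before Day 29, protocol 6.4 says that "evaluation for RRT, ordinal scale and AEs are to be completed daily through Day 29"; laboratories are not named there either.

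**Counting.** SAP 7.2.2.1 defines a treatment-emergent abnormality by "values that increase at least 1 toxicity grade from baseline at any postbaseline time point, up to and including the date of last dose" plus 30 days. With a last dose on Day 5 that runs to Day 35, past the end of required sampling. SAP 7.2.2.2 places each participant at the worst grade reached, and "the denominator is the number of participants with nonmissing postbaseline values up to 30 days after last dosing date". SAP 7.2.3 likewise uses the most severe postbaseline value for the liver tests.

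**By-visit tests.** SAP 7.2.1 states: "Baseline and change from baseline will be compared between the treatment groups using the 2-sided Wilcoxon rank sum test". Under SAP 3.8.2 the analysis visits run to Day 29.

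**The concern.** A participant discharged on Day 4 and one sampled to Day 29 carry equal weight in the percentage, although the second had far more opportunity to show an abnormality. That is harmless if time under observation is balanced between arms. It need not be balanced, because both ways of leaving observation, discharge and death, could be affected by treatment: recovery is a secondary end point and death is part of the primary one.

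The by-visit tests have a related weakness. Late visits contain mainly those not yet discharged, a group formed after randomization. A between-arm p-value there does not compare randomized groups.

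Renal safety is central to the study rationale (protocol 1.3), and renal and hepatic toxicity are named for the first data monitoring committee review (protocol 8.2.1.1). The creatinine and ALT/AST tables will therefore be read comparatively even without a formal test.

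**Working it through.** The documents state no abnormality incidence and no length of stay, so there is no plan figure to reproduce. Everything below except the planned size and the sampling rules is an assumption.

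**Model.** In both arms each inpatient day carries the same probability *h* of a first abnormality, followed by discharge with probability 1/*m* (mean stay *m* days), cut at Day 29. The proportion counted is

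P = Σ (d = 1 to 29) h·[(1 − h)(1 − 1/m)]^(d−1) = h(1 − r^29)/(1 − r), with r = (1 − h)(1 − 1/m).

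Example, h = 0.02:
- m = 10: r = 0.98 × 0.9 = 0.882, so P = 0.02 × (1 − 0.882^29)/0.118 = 16.5%.
- m = 13: r = 0.98 × 0.9231 = 0.9046, so P = 19.8%.

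| h per day | m = 10 | m = 12 | m = 13 | ratio 10 v 12 | ratio 10 v 13 |
|---|---|---|---|---|---|
| 1% | 8.9% | 10.2% | 10.8% | 0.87 | 0.82 |
| 2% | 16.5% | 18.8% | 19.8% | 0.88 | 0.83 |
| 3% | 23.2% | 26.2% | 27.5% | 0.89 | 0.84 |

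The true excess daily risk in the shorter-stay arm that would be exactly cancelled is 16–17% (10 v 12 days) or about 24% (10 v 13 days).

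**Early clustering.** If *h* decays exponentially over a mean of 3 to 6 days, the ratio moves to about 0.93–0.97.

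**Deaths.** Add an assumed in-hospital death risk of 2–3% per day on placebo, multiplied by 0.70 on remdesivir, with h = 2%:
- equal stays of 10 days: ratio 1.04–1.06, so the sign reverses;
- 10 v 12 days: 0.93–0.95;
- 10 v 13 days: 0.88–0.91.

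**Second model, using the SAP denominator.** Assume exponential discharge, placebo median stay 10 days, 2% daily risk, daily creatinine, no deaths and a discharge rate ratio of 1.3. Placebo shows 21.3% and remdesivir 18.1%. Over medians of 7–14 days, rate ratios 1.15–1.5 and daily risks 1–4%, the spurious difference is −0.9 to −7.4 points. With about 33% placebo in-hospital deaths, death hazard ratio 0.70 and 2% daily risk, it is +1.3 to +1.4 points at discharge ratio 1.0, −0.2 to −0.3 at 1.2 and −0.9 to −1.0 at 1.3.

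**Against sampling error.** Enrollment stopped before 50% of 1116, so below 558. Take 557 split 371:186 with 16.5% v 19.8%. The standard error is √(0.165 × 0.835/371 + 0.198 × 0.802/186) = 3.5 points, against a spurious difference of 3.3.

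**Early window.** In the first model (h = 2%, 10 v 13 days), counts through Day 5 are 7.9% v 8.3% (ratio 0.96), and through Day 8 they are 10.7% v 11.6% (0.93). Most of the distortion goes, but not all.

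**Per-day rates.** With constant *h*, dividing by observed days removes the difference. With early clustering it creates one the other way: a spurious rate ratio of 1.08–1.17 against the shorter-stay arm.

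**Late visits.** Ignoring deaths, the share still in hospital on Day d is (1 − 1/m)^(d−1). For m = 10 v 13 this is 0.9^7 = 48% v 57% on Day 8, and 0.9^28 = 5% v 11% on Day 29.

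**The case against.** **Direction.** A reader might infer that the plan will make remdesivir look safer because it is meant to shorten stay. The documents do not support that. No visible end point is length of stay, and recovery includes category 3, which is still in hospital. Prevented deaths lengthen observation and can reverse the sign. Protocol 1.4 does report that "approximately a third of participants were discharged prior to completion of 5 days RDV therapy", but this describes remdesivir-treated participants with moderate disease in another study and shows no difference between arms here. This objection stands.

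**Size.** Stay and daily risk are assumed, and dosing lasts at most five days, so early clustering is plausible and the bias is then small. This stands too.

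**Existing coverage.** Adverse events are collected throughout follow-up, RRT-free days are compared between arms, and renal and hepatic events are listed. A programming rule for peak creatinine exists, but the section that would use it is not visible, so a gap in renal analyses cannot be inferred. This coverage helps only in part: protocol 7.6 keeps clinically insignificant laboratory changes out of adverse events, and a rise nobody measures is not recorded.

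**Consequence.** The graded tables are counts and percentages with no test or decision attached, and the by-visit tests are unadjusted. That limits the harm to misleading estimates and p-values; it does not remove it.

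**Remedy.** Resting comparisons on events per observed day could do more harm than the existing table, as shown above. That stands, and the fix avoids it.

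**Conclusion.** The point holds as a weakness of presentation and analysis. Required sampling ends at discharge, counting ignores time observed, and the visible laboratory sensitivity analyses in SAP 7.2 address only RRT and anticoagulants. If observation time differs by arm, the arm observed for less time looks better with no drug effect.

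For assumed mean stays of 10 versus 12–13 days and no deaths, the spurious ratio is about 0.82–0.89 under constant risk and 0.93–0.97 under early clustering. Fewer deaths with equal discharge give 1.04–1.06. At the reduced size these shifts are often within sampling error. The documents support neither a claim that the table favours remdesivir nor a claim that a harm is being hidden; they support only that the table cannot separate drug effect from observation time. The later by-visit p-values have the selection problem whichever arm leaves hospital sooner.

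**What to change.** In SAP 7.2.2.2 keep the any-time table. For creatinine, ALT/AST and Grade 3–4 abnormalities, add:

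- (a) days under laboratory observation, by arm;
- (b) counts through Day 5, and through Day 8 to include values after dosing, with a note that discharge still truncates these windows slightly;
- (c) time from first dose to first abnormality, censored at discharge or last sample, with death as a competing event. State the assumption that discharge is unrelated to later laboratory risk.

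Do not rest between-arm statements on constant-rate per-day figures.

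In SAP 7.2.1, show the number still sampled at each visit, and present visits after Day 5 descriptively without between-arm p-values.

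This needs only sample, discharge and death dates, and no new data collection. The cost is a little more programming and the loss of some late-visit p-values.
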